## **24.0 Setting**

This research will take place in the Physical Therapy Faculty Practice located at [name] in Chicago.

Informed consent and authorization will be obtained after eligibility screening has been confirmed, either during the routine patient visit at the outpatient Exercise Testing or Cardiac Rehabilitation Programs.

Subjects expressing interest in participating in the study will communicate to key research personnel conducting the screening and consenting process. During the routine visit, oral consent will be obtained so that eligibility screening.

An alteration of consent and a waiver of documentation of consent will be obtained for the eligibility screening.

All investigators/study personnel carrying out recruitment will follow a detailed informed consent process that will include a careful review study requirements and explanation of the study protocol

PI, and Key Research Personnel (research assistants) will obtain consent. Beside the PI and Co-Is, study staff thoroughly trained by the PI in the consenting process, and who have completed their CITI and HIPPA training may also obtain consent from subjects.

After consent obtaining the first appointment for baseline measurements will be determined and research procedures detailed in section 11.0 will be carried out.

## **25.0 Resources Available**

**25.1** [name] runs UIC's Cardiac Rehabilitation program and sees patients undergoing CABG, history of percutaneous coronary interventions, heart failure, and/or myocardial infarction on a daily basis. This service line will provide the volume of participants to complete the study. [name] is a visiting international scholar that has 100% of his time dedicated to this study and will therefore be able to oversee study visits and collect data.

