#### **4.0 Study Endpoints\***

- 4.1** Primary endpoints; inspiratory muscle function, endothelial function, arterial stiffness.
- 4.2** Secondary endpoints; dyspnea, functional exercise capacity.

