#### **5.0 Study Intervention/Investigational Agent**

**5.1 Description of the study intervention:** Based on the findings of a systematic review (Z. Sadek et al., 2018), it has been determined that to achieve significant improvements in inspiratory muscle strength, the threshold pressure for inspiratory muscle training (IMT) should be set at 60% of the maximal inspiratory mouth pressure (MIP). Consequently, the intervention protocol for IMT involves using a threshold-loaded IMT device (Threshold IMT Philips® Resironics, Inc). In the IMT group, the initial intensity of the inspiratory threshold will be set at 60% of each patient's initial maximal MIP, which is then readjusted after 2 weeks of training to maintain the 60% of MIP throughout the 4-week period. Rates of perceived inspiratory effort on a modified Borg scale will also be used to determine the highest tolerable load for each patient (at the 4-6 level of 10) (Borg, 1982; Wilson and Jones, 1989). Patients will perform IMT for 2 sets of 30 repetitions, with one-minute intervals between each set (McConnell, 2013; Z. Sadek et al., 2018). Throughout the training sessions, patients will be instructed to maintain diaphragmatic breathing. On the other hand, the Sham-control group will follow the same training program using the same device, but without any inspiratory load. Both groups will perform the training program twice a day, five days a week, for a total of 4 weeks, under the supervision of a physiotherapist (McConnell, 2013). The supervision will be conducted remotely through telerehabilitation, utilizing video calls to connect with the patients without requiring them to physically visit the healthcare facility. To familiarize the participants with the training procedure, both the IMT and Sham-control groups will undergo a session without any load on the

**PROTOCOL TITLE:** Effects of high-intensity inspiratory muscle training as a pre-cardiac rehabilitation intervention on cardiovascular functions in patients with heart disease

day of the baseline assessments. Throughout the study, all participants will visit the healthcare facility for baseline assessments, final assessments, and an additional brief assessment session at the end of the second week of training to measure MIP and readjust the loading value. The assessment to be made at the end of the 2nd week of the 4-week training seasons will only include the assessment of inspiratory muscle function described in 11.1.5.

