**11.1.6 Endothelial Function Assessment (visit #1, 4-week visit)**

A standard non-invasive method will be used to assess endothelial function. For this, flow-mediated dilation (FMD) ultrasound measurements of brachial artery flow-mediated dilatation will be performed according to standard methods with ultrasonography (ProSound α7; Aloka, Tokyo, Japan) using a multifrequency linear array transducer as previously described (Ozemek et al., 2020; Thijssen et al., 2011). Briefly, a cuff will be placed on the upper forearm and brachial artery images will be taken ~3–6 cm above the antecubital fossa. After taking simultaneous measurements of 1-min baseline brachial artery diameter and blood flow velocity, forearm occlusion will be produced by inflating the cuff to 250 mmHg for 5 minutes and then rapidly deflating it. After the release of the artery occlusion, Doppler blood flow velocity will be obtained and B-mode ultrasound brachial artery diameter images will be measured continuously for 3 minutes. Brachial artery diameter and blood flow velocity will be analyzed using an available software package (QUIPU SRL, Cardiovascular Suite 4.5.0, Italy). All procedures will be performed following published guidelines for the assessment of FMD in human participants (Corretti et al., 2002; Thijssen et al., 2011).

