## **11.2      *Inspiratory Muscle Training Protocol:***

Based on the findings of a systematic review (Z. Sadek et al., 2018), it has been determined that to achieve significant improvements in inspiratory muscle strength, the threshold pressure for inspiratory muscle training (IMT) should be set at 60% of the maximal inspiratory mouth pressure (MIP). Consequently, the intervention protocol for IMT involves using a threshold-loaded IMT device (Threshold IMT Philips® Resironics, Inc). In the IMT group, the initial intensity of the inspiratory threshold will be set at 60% of each patient's initial maximal MIP, which is then readjusted after 2 weeks of training to maintain the 60% of MIP throughout the 4-week period. Rates of perceived inspiratory effort on a modified Borg scale will also be used to determine the highest tolerable load for each patient (at the 4-6 level of 10) (Borg, 1982; Wilson and Jones, 1989). Patients will perform IMT for 2 sets of 30 repetitions, with one-minute intervals between each set (McConnell, 2013; Z. Sadek et al., 2018). Throughout the training sessions, patients will be instructed to maintain diaphragmatic breathing. On the other hand, the Sham-control group will follow the same training program using the same device, but without any inspiratory load. Both groups will perform the training program twice a day, five days a week, for a total of 4 weeks, under the supervision of a physiotherapist (McConnell, 2013). The supervision will be conducted remotely through telerehabilitation, utilizing video calls to connect with the patients without requiring them to physically visit the healthcare facility. To familiarize the participants with the training procedure, both the IMT and Sham-control groups will undergo a session without any load on the day of the baseline assessments. Throughout the study, all participants will visit the healthcare facility for baseline assessments, final assessments, and an additional brief assessment session at the end of the second week of training to measure MIP and readjust the loading value. The assessment to be made at the end of the 2nd week of the 4-week training seasons will only include the assessment of inspiratory muscle function described in 11.1.5.

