## **13.0 Sharing of Results with Subjects\***

**13.1** Results (study results or individual subject results, such as results of investigational diagnostic tests, genetic tests, or incidental findings) will not be shared with subjects or others (e.g., the subject's primary care physicians). Only the involved researchers will be informed. Patients will not be informed about the change in MIP values.

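### No masking of outcome assessors or readers is specified, and the described workflow makes unmasked assessment likely, chiefly for MIP

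*Protocol*

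**What the plan says.** Protocol section 4.1 lists "Primary endpoints; inspiratory muscle function, endothelial function, arterial stiffness". Dyspnea and functional exercise capacity, the latter measured by the 6-minute walk, are secondary.

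On the arms, section 5.1 says that "the Sham-control group will follow the same training program using the same device, but without any inspiratory load". The IMT arm trains at 60% of MIP, and that load is reset after two weeks. All participants attend "an additional brief assessment session at the end of the second week of training to measure MIP and readjust the loading value". Section 11.2 adds that the week-2 assessment "will only include the assessment of inspiratory muscle function described in 11.1.5".

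On staff, section 25.0 says that one scholar, fully dedicated to the study, "will therefore be able to oversee study visits and collect data". Training takes place "under the supervision of a physiotherapist", remotely by video call. Sections 22.0 and 23.0 mention the principal investigator, co-investigators and research assistants, in connection with consent.

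On measurement, section 11.1.5 defines MIP as the highest pressure recorded by the device on inspiration. Section 11.1.6 has ultrasound images acquired at visit 1 and week 4, and says "Brachial artery diameter and blood flow velocity will be analyzed using an available software package". Section 11.1.7 uses tonometry at four arteries, with averaged, ECG-gated waveforms.

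Two safeguards come closest to masking. In section 10.0 the randomisation sequence is generated by an investigator with no other role. Section 13.1 says "Patients will not be informed about the change in MIP values". Neither the available protocol text nor the SAP mentions masking of assessors, image readers, the physiotherapist or the analyst.

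**The concern.** A sham arm protects the comparison on the patient's side. It protects the measurements only if those who take and read them do not know the arm. Here the plan puts an outcome measurement and an arm-revealing task into one session, and gives one person a broad role across visits and data collection.

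The outcomes are open to influence in different ways:

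- **MIP** is a maximal voluntary effort, so encouragement matters. Section 11.1.5 gives no number of efforts, repeatability rule or encouragement script.
- **The 6-minute walk** also depends on the patient's effort.
- **FMD and PWV** depend on how the operator acquires the images and waveforms.

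Section 2.2 predicts improvement with IMT, so an assessor's expectation would tend to push results that way. The trial as planned could neither detect nor remove such a bias afterwards.

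**Working it through.** **Step 1. Does the week-2 session reveal the arm?** Section 5.1 has MIP measured and the load readjusted in the same session. The sham arm has no load. A person who does both tasks therefore learns the arm. A person who only measures MIP does not learn it from that task.

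**Step 2. Which outcomes does this reach?**

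| Outcome | Status | Measured | Route of exposure |
|---|---|---|---|
| MIP | primary | visit 1, weeks 2 and 4 | direct, if one person measures MIP and resets the load |
| FMD | primary | visit 1, week 4 | only if that person also acquires or reads week-4 data |
| PWV | primary | visit 1, week 4 | same as FMD |
| 6-minute walk | secondary | visit 1, week 4 | only if that person also runs the week-4 test |

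Section 25.0 makes the week-4 overlap likely, because it excepts no visit. It does not state the overlap.

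**Step 3. Do the existing safeguards close the gap?** Independent generation of the sequence concerns how the allocation list is made, not who sees the allocation later. Withholding MIP changes from patients acts on patients. Neither masks an assessor.

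**Step 4. The plan's sample size, used only to find a plausible SD.** Section 9.1 gives 20 per group, 5% significance, 90% power and a 23 cmH2O difference. It gives no SD, so the 20 cannot be reproduced independently. Solving the two-sided normal formula for the SD:

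SD = 23 / [(1.960 + 1.282) × √(2/20)] = 23 / (3.242 × 0.3162) ≈ 22.4 cmH2O.

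The t-test version gives about 21.9. As a check, n = 2 × SD² × (1.960 + 1.282)² / 23² gives 13, 20 and 27 per group for SDs of 18, 22 and 26. I use 22 as the centre and 18 to 26 as the range.

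**Step 5. Illustration for MIP.** Suppose there is no true effect and unmasked assessment shifts MIP by b cmH2O between arms. The size of b is assumed; nothing in the documents gives it. For a two-sided 5% t-test with 20 per arm (38 degrees of freedom), the noncentrality is b / [SD × √(2/20)]. With b = 5 and SD = 22 this is 5 / (22 × 0.3162) ≈ 0.72. The resulting rejection probabilities are:

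| Bias b (cmH2O) | b / 23 | SD 18 | SD 22 | SD 26 |
|---|---|---|---|---|
| 2 | 9% | 6.4% | 5.9% | 5.6% |
| 5 | 22% | 13.7% | 10.8% | 9.1% |
| 10 | 43% | 40.2% | 28.9% | 22.0% |

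This is an unadjusted comparison. Protocol section 17.1 plans ANCOVA and the SAP plans ANOVA of change. Their residual SDs would differ, but neither analysis removes a bias that arises at the post-treatment measurement.

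**The case against.** The strongest reply is that the documents are silent, and silence is not a plan to assess unmasked. A reader might infer that the primary outcomes are assessed unmasked, or that one staff member resets the load and then takes all week-4 data. The documents support neither. Section 25.0 is a resources statement about what one person is able to do. It does not say that this person is the only assessor, resets the load or knows the allocation, and it does not mention week 4. Other personnel exist. The front pages were not available for this review, so a masking statement there cannot be ruled out. This objection stands, and it limits the point to likelihood.

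A second reply is that the week-2 session covers inspiratory muscle function only, so it does not in itself unmask FMD or PWV. This also stands. In addition, FMD is analysed by software, stiffness waveforms are averaged and MIP is recorded by a device. These features limit reading bias. They do not address how the images and waveforms are acquired or how a maximal effort is coached, and no coding of files is described. The documents do not set out the manual reading steps, so no particular one can be assumed.

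A third reply is that the error rates rest on an invented bias and a back-solved SD, cover MIP only, and say nothing about the vascular outcomes that carry the hypothesis. That is correct. They are an illustration, and at 2 cmH2O the effect is negligible.

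Finally, it should not be assumed that the physiotherapist can take over the week-2 load setting. The protocol describes that person as supervising remotely and does not say that they are someone other than the scholar in section 25.0. Existing staff may or may not suffice.

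**Conclusion.** The concern holds as a gap in the specification combined with a workflow that makes unmasked assessment likely. It is strongest for MIP, which is measured in the session where the load is readjusted. For FMD, PWV and walking distance it is conditional on the same person also taking the week-4 measurements.

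The size is not known. On the assumptions shown (no true effect, 20 per arm, SD 18 to 26 cmH2O, unadjusted two-sided t-test), an assumed MIP bias of 2, 5 or 10 cmH2O gives a false-positive rate of about 6%, 9–14% or 22–40% instead of 5%. No corresponding figure can be given for FMD or PWV, because the documents give no effect size or SD for them.

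The conclusion does not depend on those rates. It rests on the combined week-2 session, the breadth of one person's role and the absence of any stated assessor masking in the available text. If the unavailable pages do contain a masking statement, it would still have to be reconciled with the week-2 session.

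**What to change.** 1. **Reading of FMD and PWV.** Store the images and waveforms under random codes assigned by someone who does not read them. Analyse them in batch, blind to arm and visit. This protects the reading even if acquisition cannot be masked.
2. **Week-2 session.** Where existing personnel allow, have a team member other than the outcome assessor do the load-readjustment step in both arms, out of the assessor's sight. Going through the step in the sham arm too keeps the procedure from revealing the arm. The load itself does not change.
3. **Statement of masking.** Say in the protocol who is masked (patients, assessors, readers, analyst) and who is not. If one person must do both week-2 tasks, say so and report it as a limitation.

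The cost is a file-recoding step, slightly later FMD and PWV read-outs, and a hand-off at week 2. No visit, endpoint or sample size changes. Whether the hand-off needs an extra person cannot be settled from the documents, so the sponsor should confirm it. Item 1 needs only someone other than the reader to assign the codes.

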## **26.0 Multi-Site Research\***

This is a single site study.

PROTOCOL TITLE: Effects of high-intensity inspiratory muscle training as a pre-cardiac rehabilitation intervention on cardiovascular functions in patients with heart disease

Title: High-intensity Inspiratory Muscle Training as a Pre-cardiac Rehabilitation in Heart Disease

NCT Number: NCT06127147

Date: 12/12/2023

Statistical Analysis Plan

Statistical analyses will be performed using SPSS version 21.0 (IBM, Armonk, NY). The Shapiro–Wilk test will be used to evaluate normality of the data distribution for each variable. The continuous variables will be reported as mean \pm SD, and the categorical variables will be presented in absolute frequencies and percentages. Nominal data will be compared using a Chi-square test. For comparison between the baseline and postintervention, the paired-samples t test or Mann–Whitney U test will be applied based on normality distribution. Change from the baseline values will also be calculated as the mean difference for each measure. Treatment effect and between-group comparisons will be evaluated based on mean differences using analysis of variance. Effect sizes will be provided as eta square, which are interpreted as small effect (0.01), medium effect (0.06), and large effect (0.14). The alpha value will be set at alpha = 0.05 for all outcomes.
